2. STUDY OBJECTIVES

2.1 OBJECTIVES

2.1.1 Primary Objective

In patients with severe COPD and bronchiectasis, does the addition of inhaled corticosteroids:

- Alter the microbial load of pathogens?
 - o ICS beneficial effect would lead to an expected reduction in microbial load, with less significant bacterial loads (10 colony forming units/ml or more).
 - o ICS detrimental effect, would lead to an expected increased microbial load, with significant bacterial loads (10 colony forming units/ml or more)¹².

This would be assessed between the two groups (LABA-LAMA-ICS and LABA-LAMA arms).

2.1.2 Secondary Objectives (between two arms of the study) to assess if ICS:

- 1. Are beneficial, patients will have a broadened microbial diversity in sputum microbiata and if detrimental there would be loss of this diversity¹³⁻¹⁵.
- 2. Alter sputum colour, airways and systemic inflammation. The mechanism of inhaled corticosteroids is anti-inflammatory, and the hypothesis is that inhaled

corticosteroids might improve sputum colour and reduce sputum and serum inflammation¹².

- 3. Impact on microbial and mycobial community composition as explained in endpoints section 2.
- 4. Impact on spirometry (forced expired volume in 1 second, forced vital capacity, its ratio and mid expiratory flows FEF25-75).
- 5. Impact on health status using well-validated quality of life questionnaires in bronchiectasis (COPD Assessment Tool¹⁶ and St George's Respiratory Questionnaire¹⁷).
- 6. Moderate/ severe exacerbation rate and time to first moderate/ severe exacerbation.
- 7. Investigate if addition of inhaled corticosteroid has an overall beneficial/detrimental effect to the mortality rate and whether that correlates with the microbial diversity that we are also assessing in these 2 groups.

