3.11 RANDOMISATION

3.11.1 Randomisation Procedures

Following successful completion of the 4-week washout phase, verbal reaffirmation will be sought from the patient and recorded in the medical records to collect the baseline data necessary to complete the randomisation and the exclusion criterion would be rechecked.

If still eligible, the participant would be randomised to one of the two arms of the study triple (inhaled corticosteroids/Long-acting beta agonist/long acting antimuscarinic arm) or dual bronchodilator (Long-acting beta agonist/long acting antimuscarinic arm) therapy. Allocation will be made in a 1:1 ratio of study triple: dual bronchodilator using a minimisation algorithm stratified on the following variables: prior ICS (yes/no) and prior long-term macrolides (yes, no). In order to maintain a random allocation, participants will be allocated to the group which minimises the imbalance with a pre-defined probability.

The Investigator will enter the participants data via a 24-hour secure centrally controlled web based GCP compliant central randomisation system, run by the UKCRC registered Edinburgh Clinical Trials Unit (ECTU) using a validated randomisation program and will securely backup both the randomisation seed and the randomisation allocation.

The randomisation system will provide details of the treatment allocation and a confirmatory email will be sent to the PI, RN and local Clinical Trials Pharmacy. The Trial Manager and CI will receive confirmatory treatment allocation emails for all participants at all sites.

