8.2 PROPOSED ANALYSES

Analysis

Full details of the statistical analysis will be detailed in a separate Statistical Analysis Plan developed prior to examination of any accumulated trial data. A summary of the planned analysis is given below.

Results will be presented broken by treatment allocation. Where data is categorical number and percent will be presented however where data is continuous descriptive statistics including mean, standard deviation (sd), median, q1, q3, min, max will be presented. As this is a proof-of-concept study we will present descriptive statistics for markers of interest by treatment arm at each time point as well the baseline to 1-year change. No covariates are planned to be adjusted for these analyses.

Where responses are continuous for example the level of change in cfu, comparison between groups will be made using a two-sample t-test and results of this will be presented accompanied by the mean and 95% for the difference between groups. We will present the time to first exacerbation using a Kaplan-Meier survival curve stratified by treatment allocation and present this will the accompanying log-rank statistic.

Where responses are binary i.e., presence of clinically significant change in cfu, comparisons between groups will be made using a binomial test for the comparison of proportions and accompanying this we will present the difference in proportion and 95% CI for the difference.

The number of participants experiencing adverse events and serious adverse events will be reported as well as the number of events per participant. Comparison will be made between treatment arms.

As information on AE/SAE will be captured during the washout phase prior to any dosing with study drug we will present this information separately for AE/SAE occurring prior to the first dosing and AE/SAE occurring after the first dosing.

Dropouts during the study will be reported and where available a reason for dropout will be captured. The dropout rate will be compared across both treatment arms

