Results will be presented broken by treatment allocation. Where data is categorical number and percent will be presented however where data is continuous descriptive statistics including mean, standard deviation (sd), median, q1, q3, min, max will be presented. As this is a proof-of-concept study we will present descriptive statistics for markers of interest by treatment arm at each time point as well the baseline to 1-year change. No covariates are planned to be adjusted for these analyses.

Where responses are continuous for example the level of change in cfu, comparison between groups will be made using a two-sample t-test and results of this will be presented accompanied by the mean and 95% for the difference between groups. We will present the time to first exacerbation using a Kaplan-Meier survival curve stratified by treatment allocation and present this will the accompanying log-rank statistic.

Where responses are binary i.e., presence of clinically significant change in cfu, comparisons between groups will be made using a binomial test for the comparison of proportions and accompanying this we will present the difference in proportion and 95% CI for the difference.

The number of participants experiencing adverse events and serious adverse events will be reported as well as the number of events per participant. Comparison will be made between treatment arms. As information on AE/SAE will be captured during the washout phase prior to any dosing with study drug we will present this information separately for AE/SAE occurring prior to the first dosing and AE/SAE occurring after the first dosing.

Dropouts during the study will be reported and where available a reason for dropout will be captured. The dropout rate will be compared across both treatment arms

16S and ITS data: we will summarise and visualise microbial and fungal community compositions using ordination techniques/PERMANOVA-tests, allowing for global comparisons between groups. To compare alpha diversity between samples, we will look at the richness, as well as the Shannon

Version No 2.1

Effective Date 27Jun2025

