For both datasets, the relative abundances will be calculated by dividing the sequencing reads assigned to different taxa by the total number of reads per sample.

Benjamini-Hochberg (BH) adjusted P values (q values) will be used where appropriate. A P value and a q value of 0.05 will be considered significant.

All patient samples will be subjected to a similarity-based, unsupervised hierarchical clustering approach based on absolute abundances to identify community state types/clusters.

For comparisons of group differences, a one-way analysis of variance, Wilcoxon rank-sum test, Kruskal-Wallis test, or chi-square test will be used where appropriate depending on the variable(s) tested.

Version No 2.1

Effective Date 27Jun2025

Group differences in diversity will be calculated using Wilcoxon tests and linear mixed-effect models. Associations between group and overall microbiota composition will be analysed using the adonis2 function (vegan package69), based on permutational multivariate analysis of variance (PERMANOVA)-tests. Differences between groups on the lowest taxonomic annotated level (OTU) will be tested using the metagenomeseq package in R studio or the machine learning method Random Forest, depending on the distribution of data in our cohort.

Please note: the section highlighted in grey above is outwith the scope of this document, this is being conducted elsewhere.

3. Overall Statistical Principles

The level of statistical significance will be defined as two-sided p=0.05 for all analyses unless otherwise stated.

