4.5.8 Exacerbations

Table showing the number and percent of participants with radiologically confirmed pneumonia split by treatment allocation.

Descriptive analysis split by treatment allocation, of:

- number of exacerbations requiring treatment with antibiotics and or steroids
- number of exacerbations requiring treatment with antibiotics and or steroids that also includes hospitalisation

A Kaplan-Meier survival curve stratified by treatment allocation will be presented along with the accompanying log-rank statistic for the time to first moderate or severe exacerbation where this is defined as an exacerbation requiring treatment with antibiotics and or steroids.

Version No 2.1

Effective Date 27Jun2025

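### Time to first moderate or severe exacerbation is to be reported as a Kaplan-Meier curve with a log-rank statistic but no hazard ratio or confidence interval, so no exacerbation comparison carries a measure of precision

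*SAP*

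**What the plan says.** Protocol 2.1.2 lists as a secondary objective "Moderate/ severe exacerbation rate and time to first moderate/ severe exacerbation". Protocol 8.2 gives the method: "We will present the time to first exacerbation using a Kaplan-Meier survival curve stratified by treatment allocation", with the accompanying log-rank statistic. SAP section 2 repeats that text. SAP 4.5.8 keeps the method: a Kaplan-Meier curve by arm "will be presented along with the accompanying log-rank statistic for the time to first moderate or severe exacerbation".

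Here stratification by treatment allocation means one curve per arm. It does not mean a log-rank test stratified by the minimisation factors, which protocol 3.11.1 gives as prior ICS and prior long-term macrolides. SAP section 2 also says "No covariates are planned to be adjusted for these analyses". SAP section 3 sets the criterion by which the log-rank will be read: "The level of statistical significance will be defined as two-sided p=0.05 for all analyses unless otherwise stated".

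The other exacerbation outputs in SAP 4.5.8 are a table of participants with radiologically confirmed pneumonia, and descriptive counts by arm of treated exacerbations, overall and with hospitalisation. SAP 4.5.10 refers hospitalised exacerbations back to 4.5.8.

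**The concern.** For other kinds of outcome the plan asks for an effect with an interval. Continuous outcomes get a mean difference with a 95% interval (protocol 8.2, SAP section 2). Clinically significant CFU change (SAP 4.5.1), dropout for worsening COPD and respiratory failure (both SAP 4.5.10) get a difference in proportions with a 95% CI. Time to first exacerbation gets a test statistic and a curve. Mortality in SAP 4.5.9 is treated in the same way.

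Exacerbations matter to how this trial will be read. The protocol's summary says that guidelines recommend adding ICS in patients with recurrent flare-ups, and protocol 1.1 cites a large trial in which triple therapy lowered the exacerbation rate. Participants in the dual arm go without ICS for a year. Readers will ask how far the arms differed on exacerbations, and how precisely that is known. A log-rank p value judged against 0.05 answers neither question. If it is above 0.05, it can be taken for evidence of no difference when the data are compatible with a substantial benefit or harm.

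**Working it through.** **1. The plan's own figure.** Protocol 8.1 gives 36 per group for a difference of 0.76 log units, SD 0.98, two-sided 5%, 90% power. The normal approximation gives n = 2 × (1.960 + 1.282)² × 0.98² / 0.76² = 34.9, so 35. With the noncentral t distribution, 35 per group gives 89.2% power and 36 gives 90.1%, so 36 is reproduced. With 10% dropout, 36 / 0.90 = 40 per group, 80 in total. This sizing concerns CFU change only. Neither document states an event count, hazard ratio or power for exacerbations.

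**2. Inputs for the exacerbation comparison.** From the documents: 80 participants, 1:1 allocation, 12 months of follow-up. Assumed: 30% to 90% have a first event, that is 0.30 × 80 = 24 to 0.90 × 80 = 72 events. The nearest information is the entry criterion in protocol 3.4 (two or more exacerbations, or at least one hospitalisation, in the past year), which does not fix a rate. Hence the wide range.

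**3. Precision.** With 1:1 allocation, SE(log HR) ≈ 2/√d for d events. The 95% interval around an observed hazard ratio of 1.0 is exp(±1.96 × SE):

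| Events d | SE = 2/√d | 95% CI if HR = 1.0 |
|---|---|---|
| 24 | 0.408 | 0.45-2.23 |
| 40 | 0.316 | 0.54-1.86 |
| 56 | 0.267 | 0.59-1.69 |
| 72 | 0.236 | 0.63-1.59 |

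**4. What a bare p value hides.** Take a two-sided p of 0.30 (z = 1.036) favouring one arm. The hazard ratio behind it is exp(-1.036 × SE), with 95% limits exp(-1.036 × SE ± 1.96 × SE). At 24 events this is 0.66 (0.29-1.46). At 72 events it is 0.78 (0.49-1.24). The same p value goes with either, and the p value alone does not tell the reader which.

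**5. Is the estimate consistent with the planned test?** In simulated trials of 40 per arm over 12 months with about 10% dropout, the Cox log hazard ratio differed from the estimate implied by the log-rank, (O-E)/V, by less than 0.01 on average. With a baseline rate of 1 per year and dropout hazard 0.105, expected events under no effect are 80 × (1 - exp(-1.105)) / 1.105 = 48.4, for which 2/√d = 0.287. The average Cox standard error was 0.290, so the formula in step 3 is adequate at this size.

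**6. Does stratification matter?** The same simulation (1,500 trials per setting) compared the log-rank unstratified and stratified by two factors, with assumed prevalences of 70% and 30% and an assumed log hazard ratio of 0.4 each. Under no effect it rejected in 5.0% unstratified and 4.6% stratified, with a Monte Carlo SE of √(0.05 × 0.95 / 1,500) = 0.56 points. At true hazard ratios of 0.7 and 0.5, stratifying raised power by 0.3 and 0.5 points. With non-prognostic factors it lowered power by 0.5 and 1.8 points. Stronger assumed factors gave gains of up to about 3 points. The documents give neither the prevalence nor the prognostic strength of either factor.

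**The case against.** The strongest reply is that this is one component of the eighth secondary endpoint, in a proof-of-concept trial whose primary outcome is bacterial load. Neither document claims power for exacerbations or plans to conclude that the arms do not differ, so the feared misreading concerns future reporting. That stands as to weight. It does not explain why several binary outcomes in the same trial, including two safety outcomes, get an interval and this one does not.

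Three stronger readings are tempting, and the documents do not support them.

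- A reader might infer that the size and direction of any ICS effect would go unseen. That is not so: the Kaplan-Meier curve gives event-free proportions by arm, and the counts are tabulated by arm. What is missing is a summary contrast with its precision.
- A reader might infer that a hazard ratio would let the trial separate no effect from a large one. The width in step 3 comes from 80 participants, a number set for CFU change, and it would remain.
- A reader might infer that the log-rank is invalid, or materially conservative, because it ignores the minimisation factors. Step 6 does not show this, and the plan chose openly not to adjust. Covariate adjustment is not needed to close the gap.

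**Conclusion.** The gap is real and should be closed, at moderate weight. Time to first moderate or severe exacerbation is the only exacerbation outcome in SAP 4.5.8 with a planned between-arm test, and it is reported without an effect estimate or interval. Under the assumed 24 to 72 first events, an observed hazard ratio of exactly 1.0 would be compatible with anything from 0.45 to 2.23 at the low end, or 0.63 to 1.59 at the high end. A non-significant log-rank therefore could not be read as absence of a substantial effect in either direction, and the planned output would not put a number on that uncertainty.

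The conclusion that no interval is planned rests on the text alone. The size rests on the assumed event range and on the usual approximation for the standard error under 1:1 allocation.

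**What to change.** In SAP 4.5.8, keep the Kaplan-Meier curve and the log-rank statistic. Add a Cox model with treatment arm, and report the hazard ratio with its 95% confidence interval as the main result for time to first moderate or severe exacerbation. State the censoring rule in the same place: SAP 4.5.9 gives one for death, and 4.5.8 gives none.

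Optionally, stratify both the Cox model and the log-rank by prior ICS and prior long-term macrolides. If so, record this as a departure from the no-covariates statement in SAP section 2. The expected gain is small, and an unadjusted hazard ratio already closes the gap.

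The cost is a few lines of SAP text and one model. No new data are needed, and both factors are recorded at randomisation. SAP 3.3 places the analysis after database lock, so the change should be specified before then.

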4.5.9 Mortality rate

Table showing number and percentage of participants who died during the follow-up period split by treatment allocation.

A Kaplan-Meier survival curve stratified by treatment allocation will be presented along with the accompanying log-rank statistic for the time from baseline to death or censor (this will either be the date of 12 month visit or date of withdrawal if withdrawn prior to completion).

4.5.10 Safety Endpoints

Table showing number and percent of participants dropping out from trial (IMP only or all aspects of the trial) due to worsening COPD symptoms split by treatment allocation. Comparisons between treatment allocation will be made using a binomial test for the comparison of proportions and accompanying this we will present the difference in proportion and 95% CI for the difference.

Table showing number and percent of participants with respiratory failure split by treatment allocation. Comparisons between treatment allocation will be made using a binomial test for the comparison of proportions and accompanying this we will present the difference in proportion and 95% CI for the difference.

Exacerbations resulting in hospitalisation are previously covered in 4.5.8 and will not be covered further in this section.

4.6 Adverse Events/Serious Adverse Events

The number and percent of participants experiencing at least one AE/SAE will be presented. The number of AE/SAEs experienced by each person will be presented by treatment allocation along with descriptive statistics of the number of AEs/SAEs experienced by each participant (mean, standard deviation, minimum, 25th centile, median, 75th centile and maximum) presented by treatment.

A line listing for all SAEs will be presented by treatment allocation.

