3.12.3 Reason for study withdrawal

The primary reason for study withdrawal will be recorded in the eCRF. When a subject withdraws consent, the Investigator should document the reason if known to the investigator team (if reason specified by the subject) in the eCRF.

The primary reason for study withdrawal will be categorised as:

- Adverse event as decided clinically by the PI team or after discussion with the CI.
- Study closed/terminated
- Lost to follow-up
- Pregnancy
- Withdrew consent
 - subject relocated
 - frequency of visits
 - burden of procedures
 - adverse event
 - other (specify)

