4.5 OVERDOSE

Vilanterol: An overdose would likely lead to effects that are typical for $\beta 2$ adrenoceptor agonists: tremor, headache, and palpitations. Supportive and symptomatic treatment may be indicated.

Fluticasone: Acute inhalation of doses in excess of those recommended may lead to temporary suppression of adrenal function. This does not need emergency action as adrenal function is recovered in a few days.

Umeclidinium: Acute over dosage is not expected to be a clinical problem. Warning would however be issued around usual side effects like visual disturbances, dry mouth, constipation, micturition difficulties and tachycardia. Treatment is usually observation and symptomatic management.

Other side effects to watch out for: of study drugs are likely to be minor and expected. Candidiasis is the main side effect and withdrawal from study treatment will occur if it is marked as persistent and does not respond to symptomatic treatment. Patients should receive treatment with Nystatin 100,000 units four times daily for up to 7 days if candidiasis requires symptomatic treatment. Requirement for another or additional treatment should lead to study withdrawal as alternative treatments may impact the primary outcome.

Paroxysmal bronchospasm is a rare side effect (≥1/10 000 to <1/1000) any patients experiencing this would be withdrawn from treatment, the patient will be assessed, and an alternative therapy instituted, if necessary.

If patients withdraw from the study at some during the trial and do not wish to return for study visits, contact with them will be maintained by the PI, trial manager, research nurse or research assistant to ensure resolution of adverse event(s) and their GP notified. If withdrawal is due to an AE, it will be logged as such on the Adverse Event Log.

The following table summarises the strategy to mitigate some possible side effects from the proposed IMPs.

Potential Risk of Clinical Significance		Mitigation Strategy

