9.3.3 Adverse Events to be reported on eCRF

For a complete list of the expected adverse reactions and reference safety information of the TEMPESTAS study medication, refer to section 4.8 of each SmPC in the current TEMPESTAS SmPC booklet. To better assess the events that are of special interest to the trial, the following adverse events will also be reported in the eCRF from Baseline until the Final assessment regardless of severity and seriousness:

- Any community respiratory exacerbations of COPD
- Community diagnosed pneumonias
- Any oral infection
- New respiratory conditions detected or diagnosed after study treatment administration
- Signs, symptoms, or the clinical sequelae of a suspected overdose of either study treatment or a concomitant medication any cardiovascular or cerebrovascular events

Laboratory, Spirometry and Vital Signs assessments

Deterioration as compared to baseline in CSP-mandated laboratory values, spirometry values and vital signs should only be reported as AEs if:

- They fulfil any of the SAE criteria, or
- Are the reason for discontinuation of treatment with the study intervention, or
- Are considered to be clinically relevant as judged by the investigator (which
 may include but not limited to consideration as to whether treatment or nonplanned visits were required or other action was taken with the study
 intervention, e.g., dose adjustment or study intervention interruption).

If deterioration in a laboratory value/vital sign is associated with clinical signs and symptoms, the sign or symptom will be reported as an AE and the associated laboratory result/vital sign will be considered as additional information. Wherever possible the reporting investigator uses the clinical, rather than the laboratory term (e.g., anaemia versus low haemoglobin value).

In the absence of clinical signs or symptoms, clinically relevant deteriorations in non-mandated parameters should be reported as AE(s).

Any new or aggravated clinically relevant abnormal medical finding at a physical examination as compared with the baseline assessment will be reported as an AE unless unequivocally related to the disease under study.

Events not listed in this section will be recorded in the patient medical notes.

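### SAP 4.6 pools adverse events and lists only the serious ones, so non-serious oral infection and non-serious, radiologically unconfirmed pneumonia cannot be identified by arm

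*SAP*

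**What the plan says.** SAP 4.6 has three outputs. The first is a pooled count: "The number and percent of participants experiencing at least one AE/SAE will be presented". The second is the number of events per person by arm, with descriptive statistics. The third is a listing restricted to serious events: "A line listing for all SAEs will be presented by treatment allocation". It has no table by event type and no listing of non-serious events.

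The protocol collects more than these outputs can show. Section 9.3.3 names events of special interest and says "the following adverse events will also be reported in the eCRF from Baseline until the Final assessment regardless of severity and seriousness". The list includes "Any oral infection", community-diagnosed pneumonia and "Any community respiratory exacerbations of COPD". Protocol 4.5 expects side effects to be minor and states "Candidiasis is the main side effect". On candidiasis that needs more than nystatin it adds: "Requirement for another or additional treatment should lead to study withdrawal as alternative treatments may impact the primary outcome". The risk table in the same section requires every pneumonia diagnosis, radiographically confirmed or not, to be reported as an adverse event or serious adverse event.

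**The concern.** Under Protocol 4.2 both arms receive umeclidinium and vilanterol, and fluticasone furoate is the only drug that differs. The trial asks whether adding it helps or harms. A known local effect of the steroid and a class concern such as pneumonia are therefore the events a reader will look for by arm.

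Candidiasis is expected to be minor, so most cases would fall outside the listing of serious events and enter only a total shared with every other adverse event. Followed as written, the SAP could not report how many participants in each arm had the side effect that the protocol calls the main one and ties to a withdrawal rule.

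**Working it through.** This is a question of coverage, so the check sets each event against each planned output.

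**Outputs that show an event type by arm**
- SAP 4.5.8: radiologically confirmed pneumonia; exacerbations treated with antibiotics or steroids, and those with hospitalisation.
- SAP 4.5.9: deaths.
- SAP 4.5.10: respiratory failure; dropout for worsening COPD.
- SAP 4.6: serious events, through the listing.
- SAP 4.7: withdrawals, with reason if available.

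Two further provisions only re-cut the same totals: the view by treatment received (SAP 3.1) and the split before and after first dosing (protocol text reproduced in SAP section 2).

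**Oral infection**
1. If serious, it is in the listing.
2. If not serious, no row in 4.5.8, 4.5.9 or 4.5.10 applies, and 4.6 only adds it to a total.
3. If it leads to withdrawal, 4.7 gives the reason, but the category in Protocol 3.12.3 is "Adverse event as decided clinically by the PI team or after discussion with the CI". That category does not require candidiasis to be named.

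A non-serious case is therefore counted but not identifiable.

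**Pneumonia**
1. If radiologically confirmed, it is in the 4.5.8 table.
2. If serious, it is in the listing.
3. If neither, it must still be reported under Protocol 4.5. It may be counted as a treated exacerbation in 4.5.8, but it is nowhere shown as pneumonia.

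**COPD exacerbations.** Protocol 9.3.2 says that events consistent with expected progression are not recorded as adverse events. Protocol 9.3.3 lists community exacerbations as reportable. The SAP does not say whether its adverse event totals include them.

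**Scale, for orientation only.** Protocol 8.1 plans 36 per arm, and 36 / 0.9 = 40 per arm after 10% dropout. The Protocol 4.5 risk table gives pneumonia rates of 3% on vilanterol alone and 6–7% on fluticasone furoate/vilanterol. This is a different comparison in a different population. Applied to 40 per arm:
- without the steroid: 40 × 0.03 = 1.2 cases
- with the steroid: 40 × 0.06 = 2.4 to 40 × 0.07 = 2.8 cases

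Rounded to 1 of 40 against 3 of 40, the difference is 7.5% − 2.5% = 5.0 points. The Newcombe 95% interval uses the Wilson limits of each proportion: 2.6% to 19.9% for 3/40 and 0.4% to 12.9% for 1/40.
- lower: 5.0 − √[(7.5 − 2.6)² + (12.9 − 2.5)²] = −6.5
- upper: 5.0 + √[(19.9 − 7.5)² + (2.5 − 0.4)²] = +17.5

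The limits are calculated from unrounded values. The documents give no rate for oral infection. Assuming 1 of 40 against 4 of 40, the same method gives 7.5 points (−4.5 to +20.7). Varying the second count from 2 to 6 gives 2.5 points (−8.5 to +14.2) up to 12.5 points (−0.6 to +26.7). These intervals show how imprecise the table would be. They do not measure the gap, which is a missing row.

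**The case against.** The strongest reply is that little is at stake. Protocol 8.2 commits only to participants with events and events per participant, and SAP 4.6 delivers that. The trial is an 80-patient proof of concept, every interval above includes zero, and the data remain in the adverse event log and eCRF. Protocol 13.1 also promises a clinical study report following ICH guidelines, and the data monitoring committee has its own report outline in a charter not available here. All of this is fair and limits the weight of the point. It does not close the gap, because neither the report wording nor the committee wording in the protocol promises a table by event type.

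The pneumonia gap is also narrow. Protocol 4.5 calls for a chest X-ray read whenever pneumonia is suspected, so what remains is non-serious pneumonia with a negative X-ray or none. This stands.

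Three stronger readings are tempting, and the documents do not support them.
- **That the omission is equally serious for every event in 9.3.3.** Non-serious cardiovascular events and overdose sequelae also lack a row. But the protocol attributes cardiovascular risk to umeclidinium and vilanterol, which both arms receive, and it states no expected frequency for overdose.
- **That 9.3.2 and 9.3.3 contradict each other on exacerbations.** Section 9.3.3 reads naturally as a specific addition to the general rule. What is missing is only a sentence in the SAP saying what its totals contain.
- **That the SAP departs from the protocol.** Both documents are silent on a breakdown by type.

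**Conclusion.** The point holds as a reporting gap. As written, SAP 4.6 cannot show by arm how many participants had non-serious oral infection, or non-serious pneumonia without radiological confirmation. Serious events, confirmed pneumonia, treated exacerbations and respiratory failure are already visible by arm. The primary analysis is untouched.

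The conclusion rests on reading the SAP's list of outputs as complete for the statistical report. The expected counts are a handful per arm, so the missing table would be descriptive. The pneumonia scale assumes that rates from other studies carry over, and the oral-infection counts are assumptions. Nothing is implied about the size or direction of the pooled totals.

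**What to change.** Add one descriptive table by arm to SAP 4.6, giving participants with at least one event and number of events, by allocation and by treatment received as SAP 3.1 already requires. Use rows for the special-interest events in Protocol 9.3.3. The minimum is:
- oral infection
- pneumonia, radiologically confirmed
- pneumonia, not confirmed

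Add one sentence stating whether COPD exacerbations are included in the adverse event totals. No tests are needed. A table by MedDRA System Organ Class is optional: Protocol 9.5 provides the codes, but a class need not isolate oral infection, and 9.3.3 sends unlisted events to the medical notes.

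The cost is a few lines of SAP text and one table from data already collected. The downsides are small counts with wide intervals at about 40 per arm, and some classification work if the eCRF entries are free text. That classification should be done without sight of allocation where possible, since the trial is open label.
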